During the screening or baseline study visit, all participants will receive training to appropriately check blood pressure at home using study-issued home blood pressure monitors. A baseline chemistry panel and assessment of albuminuria will be ordered, if not completed clinically within 3 months of the study visit.

Both groups will complete an initial study visit with the study team and physician and complete a 24-hour ABPM session. The ABPM session can be done prior to training for the intervention participants.

4. Random allocation and blinding. Randomization will be 1:1 intervention/control. Randomization will be done by a central system, stratified by degree of hypertension at initial visit (> 160 systolic or below) and block-randomized by clinical sites using the centralized randomization tool through the Health Services Research Center data servers. The study participants and personnel will be unblinded. The research assistant in charge of checking blood pressures at the initial, 6-month, and 12-month visits may be aware of treatment allocation but will use standard procedures and an automated Omron cuff, using the SPRINT study blood pressure measurement protocol (5 minutes of quiet rest followed by 3 automated blood pressures at one-minute intervals, averaging last 2 to determine in-clinic BP), to ascertain blood pressures to avoid digit preference and bias.

5. Follow-up study visits: Participants in both randomization arms will then return for 6-month and 12-month study visits at which times blood pressure will be checked by a research assistant, and participants will complete questionnaires similar to those obtained at baseline, blood and urine studies for kidney function and albuminuria (as part of routine clinical care) at 12-month visit, and repeat ABPM at both 6 and 12-month visits.

6. Usual care and intervention protocols. Both groups will be issued a home blood pressure cuff with data recording capabilities identical to that in the active arm of the study, (Microlife BP, Microlife USA Inc), will meet the study physician and have questions answered, and will be instructed to record and share results with their primary care physician at routine clinic visits. The patient's and provider's willingness to titrate to a clinical goal of 130/80 (home goal of 120/75) will be confirmed.

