The **default** stepped medication self-management algorithm (**Figure**, similar to protocols used successfully at the Kaiser healthcare systems) will be reviewed and, if necessary, customized by the study physician, to include information about when laboratory tests should be done. Unless there are compelling reasons to continue current medication, participants already taking one medication will be switched to the first step medication in the study protocol. If participants are not willing to change to the study medication, or have specific indications for their current medication (e.g. beta-blocker for atrial fibrillation, ACE inhibitor for diabetes) a personalized self-management plan including their current medications or contraindications, will be discussed on an individual basis based on the initial study visit, the self-management plan will be modified as needed, and the final self-management plan will be shared with the primary care physician via co-signature-requiring notes in CPRS.

Figure. Standard medication change algorithm.

All study prescriptions will be entered by the study physician in 'suspended' status at the initiation of the study. The pharmacy system allows medications to be ordered in this status and then activated at an appropriate interval, as for for medications intended for a forthcoming procedure. Prescriptions in this mode cannot be activated without the involvement of a physician or designated pharmacist. The patient will be able to activate the steps in the protocol by calling the SMART study phone line, the study team will alert the study physician to activate the next medication. The study physician, team pharmacist, or coordinator, in turn, will alert the primary care physician to changes via mandatory co-signature and approval on notes in the medical record. This will alert the physician of an impending medication change. The primary care physician will still be the first point of contact for any in-person visits related to hypertension; any interval calls to the study team regarding blood pressure symptoms will also be routed to the primary care physician.

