8. Safety metrics. We will assess SAEs both by active chart surveillance for ER or unscheduled clinic visits for enrolled veterans as well as by interview at the study visits. The CPRS system allows automated notifications to study physicians and staff for all patients enrolled in the study, so that admissions and ER visits can be reviewed on an ongoing basis; we will compile these quarterly. Every time a new medication is requested, a chart review by study staff will be triggered to confirm that medications are not being requested too frequently (protocol violation) in the intervention arm. Participants with significant safety violations in the intervention arm, identified either through interval contact or through log reviews at the 6 month visit, will be considered to have failed self-management and will be returned to usual care. Participant-reported side effects and adverse events will be actively collected at the 6-and 12-month visits in both groups.

Potentially study-related SAEs and all hospitalizations and major events will be reviewed locally by the study physicians. An un-blinded DSMB consisting of 3 experienced nephrologist-epidemiologists and a general internist, all working in the VA system and assisted by the study statistician, will review SAEs and in clinic BP data in both groups at the point where 100

participants reach the six-month time point, and every time an additional 100 participants reach six months. Any major interval SAEs or concerns will be communicated to the lead member of the DSMB who will have the option to ask for a full review.

9. Patient oriented metrics.

The Patient-Practitioner Orientation Scale has been used in prior hypertension studies at VA and assesses patients' preferred role orientation (patient- vs. provider-centered) in their clinical encounters.

Acceptability: Acceptability of the intervention will be measured using research study retention rates, patient satisfaction questionnaires including both quantitative and qualitative ratings, and adherence measures described below. We will assess participant satisfaction using 10 questions developed by the investigators. Similar questions have been used by [name] in other studies. (See Appendix 1). Clinicians with at least 2 intervention participants in the study will be surveyed with two simple Likert-scale questions regarding their opinion of the intervention and whether they would want future patients to use a similar plan.

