At the baseline, six-month, and twelve-month visits, the blood pressure will be measured by a research protocol (3 measurements with interval pauses as above). The blood pressure from the research study visit on the day of randomization will serve as the baseline study visit for this trial. The outcome blood pressure will be the similarly measured (research protocol) blood pressure at the 12 month study visit.

ABPM set-up will be done according to our previously used Spacelabs protocols from SPRINT study.

All study instruments will be administered by research staff in-person with patients at the baseline, 6 and 12 month visits.

Chapter 8. Safety Monitoring and Reporting

The main clinical adverse events that will be monitored during this trial are those related to overor under-treatment of blood pressure. These were not different from usual care during the two studies of similar interventions in the UK, and only 3% of those in the intervention group deviated from self-titration protocols in those studies. Nevertheless, we plan to actively monitor for these issues by scheduled chart review for clinical or ER visits, hospitalizations, and potentially study-related serious adverse events (e.g. syncope, hypertensive urgency, stroke, MI, death). Other adverse events potentially related to the study will also be collected (e.g. medication side effects, abnormal laboratory findings including sodium < 130 or potassium <3 (for those on thiazide); potassium >6 for those on ACE; creatinine 50% higher than baseline).

We have assembled a DSMB for this study given the potential risks of self-management of blood pressure. This will consist of experienced nephrologist-epidemiologists and a general internist, all working in the VA system. Assisted by the study statistician they will review AEs and BP data in both groups at the point where each group of 100 participants have reached the six-month time point.

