Real-time Safety Monitoring: The DSMB lead will be informed by formal written event reports and directly by teleconference within 24 hours of any serious adverse event (SAE) deemed by the investigators to be potentially study related. The chair will make preliminary recommendations and/or call a full ad hoc meeting of the DSMB. All other related AEs and unrelated SAEs will be reported to the chair at a frequency determined by him/her, and reviewed by the full DSMB at the mid-point meetings or earlier, at the discretion of the DSMB chair. Serious adverse events will be reported to VA IRB by the investigators as required.

Data Safety Monitoring Board: The DSMB will include 3 physicians from VA institutions with statistical expertise and clinical knowledge of hypertension as well as trial experience.

All lab tests in this protocol (renal function panel, urinalysis, urine protein, urine creatinine) are used in routine care and will be reported in CPRS to both the study team and primary care physician.

Chapter 9. Data Management, Quality Control, and Statistical Considerations DATA MANAGEMENT AND STATISTICAL CONSIDERATIONS.

1. Data Management Overview. Data will be collected on paper forms and questionnaires. All forms will be coded to facilitate entry into quantitative computer database. The project coordinator and research assistant will monitor the quality of the data on a weekly basis so that prompt resolution of errors and omissions can be achieved. Coding and data entry will be done as data is collected. All data will be entered in the secure online data base, using study ID numbers. Links to identifiers will be saved internally at each site. Paper data forms will be stored in locked cabinets in the study office space.

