Hypothesis 1b: Improvement in systolic blood pressure measured by ABPM from baseline to 12 month will be greater in the intervention vs. the usual care group. For SBP measure by ABPM, we will take an average SBP over the 24 hour measurements as the outcome measure. The change in average SBP between baseline and month 12 will be compared between two intervention groups using similar analysis methods as we described for Hypothesis 1a.

Hypothesis 1c: The proportion of blood pressure reaching the 130/80 goal at month 12 in intervention group will be greater in the intervention vs. the usual care group. The outcome is a binary variable which measures whether the blood pressure was at goal. The Fisher's exact test will be used to compare the proportion of subjects with blood pressure reaching the individualized goal at month 12 between the intervention and the usual care arm. Multivariable logistic regression will be used to study the difference in outcome between two study groups with adjustment for baseline variables if randomization is unbalanced. Univariate analyses (Fisher's exact test, Wilcoxon rank sum test) will be used to assess the association between the baseline characteristics and the outcome first, then those variables that are moderately associated (p < 0.15) with the outcome or unbalanced (p < 0.10) between study groups will be included as potential covariates in multivariable model.

Hypothesis 2. Medication related SAEs and patient-reported outcomes will be similar in the two arms and there will be similar rates of ER visits and hospitalizations in the two arms. Descriptive statistics (mean, SD, median and range) will be used to summarize the number of medication related SAEs, patient-reported outcomes, number of unscheduled clinic visits, number of ER visits and hospitalizations over the 12-month study period. The difference in proportion of subjects with medication related SAEs, proportion of subjects unscheduled clinic visits, rates of patient-reported symptoms, proportion of subjects with ER visits and proportion of subjects with hospitalizations will be compared between two study groups using Fisher's exact test.

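### Hypothesis 2 compares SAEs between arms only if they are medication related, an undefined label with no named rater in an unblinded trial; an any-SAE comparison should be added beside it

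*Combined protocol and SAP*

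**What the plan says.** Chapter 9, section 2 (Data analytic plan), Hypothesis 2, expects that "Medication related SAEs and patient-reported outcomes will be similar in the two arms". The listed SAE comparison, by Fisher's exact test, is "The difference in proportion of subjects with medication related SAEs". The same sentence goes on to items with no attribution condition: unscheduled clinic visits, patient-reported symptoms, and "proportion of subjects with ER visits and proportion of subjects with hospitalizations will be compared between two study groups". No comparison of SAEs irrespective of attribution is listed, and no margin is given for similarity.

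The plan neither defines medication related nor says who decides it. The nearest text uses a different term. Chapter 2, section 8 (Safety metrics) says: "Potentially study-related SAEs and all hospitalizations and major events will be reviewed locally by the study physicians". Chapter 8 triggers urgent reports to the DSMB lead for an SAE "deemed by the investigators to be potentially study related". Chapter 8 also plans chart review for "potentially study-related serious adverse events (e.g. syncope, hypertensive urgency, stroke, MI, death", among other items.

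On blinding, Chapter 2, section 4 says: "The study participants and personnel will be unblinded". On prescribing, Chapter 2, section 6 has the study physician enter the intervention-arm prescriptions in advance. When a participant calls to take a step, "the study team will alert the study physician to activate the next medication". In usual care, the primary care physician manages hypertension and study visits involve no medication changes. The Adherence paragraph of Chapter 2, section 9, however, says the study issues medications to all participants as 30-day refills.

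**The concern.** Which SAEs enter the comparison depends on a causal judgement. In an open trial that judgement is made with allocation known, unless the plan arranges otherwise, and this plan does not. In the intervention arm, the physicians who review events also entered and activated the study drugs. In usual care, treatment is mainly in other hands. A reviewer may therefore be more ready, or less ready, to see a drug cause in one arm. The documents do not show the direction, and either is plausible.

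If attribution differs by arm, the medication-related proportions can differ when the true SAE risks do not, or agree when the true risks differ. The second case matters because Hypothesis 2 claims similarity, so a lost signal favours the claim. Some SAEs could escape the attribution-free items altogether, for example a death outside hospital. The events that Chapter 8 names have no listed comparison by arm.

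**Working it through.** **Inputs from the documents.** 1:1 allocation (Chapter 2, section 4); 200 per arm recruited and 320 completing in total (section F4, Sample size and power); Fisher's exact test (Hypothesis 2). The plan gives no SAE rate, attribution share, significance level or power for Hypothesis 2. The SAE rates and attribution shares below are assumptions. The two-sided 0.05 level is borrowed from Hypothesis 1a.

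**The plan's own figure.** The only sample size is for Hypothesis 1a: 5 mm Hg, SD 16, 80% power, 20% attrition. Per arm, n = 2 × (1.960 + 0.842)² × 16² / 5² = 160.8, so 161. Allowing for attrition, 161 / 0.8 = 201.3, so 202 per arm and 404 in total, against the stated 400. Power with 160 completers per arm is 79.8%. The figure reproduces and supports the use of 200 per arm (160 as a sensitivity check).

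**Method.** Expected medication-related rate = all-cause SAE risk × share attributed. The rejection probability is exact: the sum over all pairs of counts (i, j) of Bin(i; n, p₁) × Bin(j; n, p₂), taken where the two-sided Fisher p-value is at most 0.05.

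**Main illustration.** All-cause risk 15% in both arms: 0.15 × 200 = 30 subjects each. With 20% versus 40% attributed, 30 × 0.2 = 6 and 30 × 0.4 = 12, or 3% versus 6%. The probability of rejection is 22.5% (16.6% with 160 per arm). The all-cause difference is 0, with standard error √(2 × 0.15 × 0.85 / 200) = 0.0357 and 95% half-width 1.96 × 0.0357 = 0.070, or 7 points. Counts of exactly 6 and 12 give Fisher p = 0.23. The typical result is thus a doubled point estimate, not a significant one.

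**Creating a difference.** Equal all-cause risk, 200 per arm, probability that Fisher's test rejects:

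| All-cause risk, both arms | 30% vs 30% attributed | 40% vs 20% | 50% vs 20% |
|---|---|---|---|
| 5% | 1.2% | 4.4% | 9.6% |
| 10% | 2.2% | 13.1% | 27.0% |
| 15% | 2.8% | 22.5% | 44.6% |
| 20% | 3.0% | 31.7% | 59.3% |

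With 160 per arm, the last column runs from 6.1% to 48.2%.

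**Hiding a difference.** Suppose true all-cause risks of 20% and 10%, with 200 per arm.
- All-cause test: power 77%.
- Medication-related test, 30% attributed in both arms (6% vs 3%): 22.5%.
- Medication-related test, 20% attributed in the higher-risk arm and 40% in the other (4% vs 4%): 2.6%.

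For 10% versus 5%, the three figures are 41%, 8.9% and 1.7%.

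**What an all-cause test loses.** Suppose attribution is accurate and the whole excess is drug-related. Start from 15% all-cause with 20% of it attributed, so 3%. If medication-related SAEs triple to 9%, all-cause rises by 6 points to 21%. Power is 66% for 3% vs 9% and 30% for 15% vs 21%. For a doubling (3% vs 6%, 15% vs 18%), it is 23% and 10%.

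**The case against.** The strongest reply is that the plan already contains attribution-free safety comparisons. Unscheduled visits, ER visits and hospitalizations are tested by arm, and the statement of Hypothesis 2 itself names ER visits and hospitalizations. Most serious events would appear there. This stands. A reader might infer that the whole safety conclusion depends on attribution, and the documents do not support that. What remains is narrower. Those items count health-care contacts and not seriousness, they can miss an SAE without a contact, and they do not show the named events separately.

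A reader might also infer that study physicians assign the medication-related label and that they prescribe in one arm only. Neither is stated. The text gives them local review of events and gives investigators a judgement of study relatedness for reporting. That they also apply the label is a reasonable inference. The separation of prescribing by arm fits Chapter 2, section 6, but the sentence on 30-day refills for all participants must be reconciled with it, and primary care may change medication and co-signs changes in the intervention arm. Nor does the use of study related in the monitoring text show that the tested label cannot apply in usual care, since both arms receive antihypertensive treatment.

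Third, the DSMB sees SAEs in both groups and also receives unrelated ones (Chapter 2, section 8; Chapter 8). That is so, but it is monitoring by an unblinded board and does not supply a comparison for the final analysis.

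Finally, all-cause events dilute drug-specific harm, and the last step of the working shows that the loss can be large. This objection stands against replacing the medication-related test or reducing it to description. It does not stand against adding a comparison beside it.

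**Conclusion.** The point holds in limited form. The plan's only SAE comparison is filtered by a label that has no definition and no named rater, in a trial where those likely to apply it know the allocation. Attribution could create or hide a difference on this one item. That it would differ by arm is an inference from the roles described, not something the documents show.

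The size depends wholly on assumed rates. At an equal 15% SAE risk and 20% versus 40% attributed, false rejection is about 23%, against under 3% when attribution is equal. Over the scenarios shown at 200 per arm with unequal attribution, it runs from about 4% to 59%. In the opposite direction, power for a true 20% versus 10% can fall from 77% to under 3%. The medication-related test is a legitimate choice for drug-specific harm. The weakness is that it is the only SAE comparison.

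**What to change.** Add to Hypothesis 2 the proportion of subjects with any SAE over 12 months, whatever the attribution, by arm, with the risk difference and 95% CI. Add the events named in Chapter 8 (syncope, hypertensive urgency, stroke, MI, death) in the same form. Keep the planned medication-related SAE test beside these, define the label once for both arms, and state who applies it. Reconcile the Adherence sentence on issuing medications to all participants with the usual-care description in Chapter 2, section 6.

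The cost is SAP wording and one more table. SAEs are already under ongoing review for all participants in the measures table, and unrelated SAEs are already reported to the DSMB chair, so no extra visits or staff are needed. The drawback is that all-cause events dilute drug-specific harm, which is why the medication-related test stays. Label: cheap improvement.

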The theoretical requirements will be assessed using paper-based exercises, as well as verbal questions and answers based around case scenarios. A training form that includes details of the assessment scores will be completed by the trainer to ensure the patient has successfully satisfied all areas of the assessment. For those patients who do not successfully satisfy all areas of the assessment, an additional training session will be arranged after discussion with the study physician.

If participants are unable to self-monitor their blood pressure after 2 trainings, it will be explained to them that they will be unable to participate in self-management; they will continue in the study, in an intention to treat fashion, but will not self-manage. The reason for this will be recorded on the training form.

Making Medication Changes

Medication changes will only apply to blood pressure medication and will involve either:

- Increasing the dose of current medication, or
- Starting to take a new medication, usually in addition to the ones the patient already takes

During the final step in training, the participant will meet with the study physician to learn when and how to adjust their medication by learning the self-titration algorithm. (See attached Patient Training SOP)

Agents available for the self-titration algorithm

The preferred titration scheme is:

Amlodipine 5 mg Amlodipine 10 mg Amlodipine 10 mg plus HCTZ 12.5 mg/Lisinopril 10 mg (combination pill) Amlodipine 10 mg plus HCTZ 25 mg/Lisinopril 20 mg (combination pill)

This 4 step plan was chosen for several reasons:

- 1) It starts with an agent that does not require monitoring of chemistry panels
- 2) It includes the 3 preferred classes of antihypertensive agents after step 2
- 3) It includes only 2 different physical pills

Although there is a preferred standard titration scheme, there will be participants for whom switching from current single medication to amlodipine is not feasible (or who are already taking larger doses of amlodipine); for whom prior history precludes use of one of these three agents (note that an 'allergy' is not the only reason to preclude use of a medication, e.g. chart must be reviewed for hyponatremia in setting of HCTZ in past); for whom there are reasonable expectations of drug interactions, etc.

For these participants, the study physicians at each site will choose a reasonable titration algorithm, also including two different drugs, and 4 titration steps as above.

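### Scheduled laboratory values and collected laboratory adverse events have no stated between-arm analysis, so kidney or electrolyte harm without an SAE, symptom or visit is absent from the Hypothesis 2 comparison

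*Combined protocol and SAP*

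**What the plan says.** **Safety comparison.** Chapter 9, Hypothesis 2, predicts that "Medication related SAEs and patient-reported outcomes will be similar in the two arms and there will be similar rates of ER visits and hospitalizations". The comparisons it then lists are "The difference in proportion of subjects with medication related SAEs, proportion of subjects unscheduled clinic visits, rates of patient-reported symptoms", followed by "proportion of subjects with ER visits and proportion of subjects with hospitalizations will be compared between two study groups using Fisher's exact test". It names no laboratory value, no laboratory abnormality and no overall count of non-serious adverse events. It gives no margin for similarity.

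**Laboratory data.** The schedule tables in Chapter 2 and section 4.3 place a chemistry panel and urine albumin/creatinine at screening and month 12, with the chemistry panel as needed in between. Chapter 2, section 3, says of entry: "A baseline chemistry panel and assessment of albuminuria will be ordered, if not completed clinically within 3 months of the study visit". Section 5 says "Participants in both randomization arms will then return for 6-month and 12-month study visits", with "blood and urine studies for kidney function and albuminuria (as part of routine clinical care) at 12-month visit". Under section 6, usual care participants complete the same study measures.

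**Anticipated laboratory harm.** The default titration scheme in Chapter 4 brings in HCTZ and lisinopril at its third and fourth steps. One reason given for the scheme is: "It starts with an agent that does not require monitoring of chemistry panels". Chapter 2, section 6, requires a chemistry panel when a Step 3 or Step 4 drug is requested. Chapter 8 states: "Other adverse events potentially related to the study will also be collected". Its examples include sodium below 130, potassium below 3 (on a thiazide), potassium above 6 (on an ACE inhibitor) and creatinine 50% above baseline.

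**The concern.** The protocol identifies kidney and electrolyte effects as possible consequences of the drugs in its algorithm, and it schedules the measurements that would show them. The analysis plan then leaves those measurements unused. A rise in creatinine or a shift in potassium that leads to no SAE, reported symptom, unscheduled visit, ER visit or admission has no route into any Hypothesis 2 endpoint.

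The collected laboratory adverse events do not fill this gap well, even if someone tabulates them. Between visits, testing in the intervention arm is triggered by Step 3 and Step 4 requests, while in usual care it is left to the primary care physician. Some of the limits are also tied to the drug being taken, which is decided after randomization. The month-12 panel is the only follow-up laboratory measurement that the calendar places at the same point for both arms. What is at stake is the completeness of the safety result, not the blood pressure result.

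**Working it through.** **1. Search of the analysis plan for a laboratory analysis**

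| Part of Chapter 9 | What it analyses | Laboratory values? |
|---|---|---|
| Data analytic plan, opening | distributions, baseline comparisons, missing data, ABPM and home BP handling | no between-arm outcome analysis |
| Hypotheses 1a to 1c | clinic SBP, ABPM SBP, proportion at goal | no |
| Hypothesis 2 | medication-related SAEs, patient-reported outcomes and symptoms, unscheduled visits, ER visits, hospitalizations | no |
| Hypothesis 3 | acceptability, self-efficacy, other scores | no |
| Data safety monitoring | adverse events, protocol violations, BP averages and home logs for the DSMB | no laboratory comparison; interim only |

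**2. The plan's own figure.** The only sample size calculation is for SBP: difference 5, SD 16, two-sided 0.05, 80% power, 20% attrition.
- n per arm = 2 × (1.960 + 0.842)² × (16/5)² = 2 × 7.85 × 10.24 ≈ 161. Then 161/0.80 = 201.25, rounded up to 202.
- The plan states 160 completers and 200 recruited per arm. Power at 160 per arm is 0.798. The figure reproduces, and it supplies the 160 per arm used below. It does not bear on the omission.

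**3. What the scheduled panel could estimate.** The documents give no laboratory SDs, so those below are assumptions for change from entry. Adjusting for the entry value should not widen these intervals materially.
- 95% half-width = 1.96 × SD × √(2/n). At n = 160 this is 0.219 × SD.
- eGFR: SD 8, 10, 12 gives ±1.8, ±2.2, ±2.6 mL/min/1.73 m².
- Potassium: SD 0.35, 0.4, 0.5 gives ±0.08, ±0.09, ±0.11 mmol/L.
- Sodium: SD 2.5, 3 gives ±0.55, ±0.66 mmol/L.
- The 160 assumes that every completer has a panel. For eGFR with SD 10, 120 panels per arm gives 19.6 × √(2/120) = 2.5, and 100 gives 19.6 × √(2/100) = 2.8.

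**4. What threshold counts could show.** The documents give no laboratory event rates, so these are also assumed. With 160 per arm and an exact Fisher test at two-sided 0.05:

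| Usual care rate | Power against a doubling | 95% half-width if rates are equal, 1.96 × √(2p(1−p)/160) |
|---|---|---|
| 1% | 3% | 2.2 points |
| 2% | 10% | 3.1 points |
| 5% | 32% | 4.8 points |

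Threshold counts alone would say little, which favours the continuous estimates.

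**5. Why unscheduled results should be kept apart.** If each test has an assumed 2% chance of an abnormal result, independently, one extra test raises the proportion detected from 2.0% to 1 − 0.98² = 4.0% with no true difference. At 1% and 5% it rises to 2.0% and 9.8%.

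**The case against.** The strongest reply is that Hypothesis 2 does what it says. It predicts similarity for a stated list of events and compares those events. A reader might infer that the trial claims overall safety equivalence and omits the evidence. The documents make no such claim, and that reading should be dropped.

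A reader might also infer that non-serious laboratory harm never reaches the result. That is too strong. Chapter 2, section 8, collects side effects and adverse events in both groups at months 6 and 12, and harm that produces a symptom or visit is counted, though only as that symptom or visit. Nor do the documents show that such harm is usually silent or seldom leads to events within a year; they give no laboratory event rates.

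Nor is this a failure of monitoring. Abnormal results go to primary care with study physician oversight, and the DSMB reviews adverse events in both groups. That review is interim, however, and is not a final between-arm result.

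Finally, the month-12 panel is less even-handed than the calendar suggests. It is drawn in routine care. Entry tests are clinical orders made with the primary care physician's agreement, and recent clinical results are accepted. Completion may differ by arm. A month-12 value may also follow correction of an earlier abnormality, and so may understate what happened.

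These points limit the claim and shape the remedy. They do not supply the missing analysis.

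**Conclusion.** The point holds in a limited form. Laboratory values are scheduled at entry and month 12 in both arms, laboratory adverse events are collected, and the plan states no between-arm analysis of either. The consequence is confined to kidney or electrolyte harm that causes no SAE, symptom or visit: Hypothesis 2 as written cannot show it. The documents do not say how often that occurs, so the effect on the trial's conclusions cannot be sized.

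What can be sized is the information left unused: about ±2.2 mL/min/1.73 m² for the eGFR difference, or ±2.5 to ±2.8 with fewer panels. This rests on an assumed SD of 10 and on 160, or 120 to 100, panels per arm. The primary outcome is untouched. This is a cheap improvement to the safety analysis, and the added results would inform a judgement on similarity without establishing it.

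**What to change.** Add to Hypothesis 2, labelled as supportive safety estimates:

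- The between-arm difference with 95% CI in month-12 eGFR (or log creatinine), potassium, sodium and log albumin/creatinine ratio, each adjusted for its entry value, by randomized arm. State that no margin is defined and that these estimates do not prove similarity.
- Descriptively, with 95% CI, the proportion in each arm whose month-12 value meets the Chapter 8 numerical limits. For this analysis, apply the limits to everyone whatever drug they take, so that the comparison stays randomized. Note that events may be too few for a useful test.
- The number with an entry and a month-12 panel, by arm, and a missing-data sensitivity analysis in line with the Data analytic plan. Imputation from clinic sources suits laboratory data better than last observation carried forward. Where only the entry value exists, carrying it forward sets the change to zero and so favours similarity.
- Unscheduled results reported separately with the number of tests per arm, and a statement that month-12 values may follow correction of earlier abnormalities.

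The cost is SAP wording and a few extra models on data already scheduled. No visit, test or clinical rule changes. The downside is some missing values, because the panel is drawn in routine care.
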